4.3.2. Optional Extended Use Treatment Period

Selection of once-daily inhalation of TPIP at 80 – 640 µg was based on clinical PK and safety data from healthy participants, predicted efficacious dose levels using pre-clinical data, safety margin from rat and dog NOAEL doses, and Tyvaso® clinical experience.

In Phase 1 studies, TRE PK was linear, and the systemic exposure was dose proportional. Single doses of up to 675 µg and multiple doses of up to 225 µg TPIP QD for 7 days were generally well tolerated. Most AEs observed were mild in severity and consistent with the safety profile of other prostanoïd therapies.

Based on exposures following a single dose of TPIP 675 µg in Study INS1009-102, TRE exposures in this study are not anticipated to exceed those following administration of the currently approved treprostinil product, Remodulin®. Treprostinil exposures following a continuous IV infusion of 10 ng/kg/min Remodulin (C_{max} 1,470 pg/mL; AUC 25,690 pg*h/mL) are reported to be 2.1-fold and 4.7-fold higher, respectively, than those observed following administration of TPIP 675 µg (C_{max} 717 pg/mL; AUC 5,480 pg*h/mL) ([Laliberte et al., 2004](#)). Minimal accumulation was observed following repeat doses of TPIP 225 µg QD for 7 days, and since a lower maximum dose (640 µg) will be used in the extended use portion of this study,

TRE exposures are expected to be lower than those observed following single doses of TPIP 675 µg in Study INS1009-102.

Based on the findings above, the TPIP dose will range from 80 µg to 640 µg QD in this treatment period.

4.4. Study Completion

A participant will be considered to have completed the study if he/she has completed the Study Day 30 safety follow-up (shown in [Table 1](#)) and has not elected to enter the optional EUT period. A participant who has entered the optional EUT period will be considered to have completed the study if he/she has completed the EUT period safety follow-up (EUT Day 142). The study will be considered completed on the date of the last safety follow-up of the last participant in the study.

5. STUDY POPULATION

The study is expected to recruit approximately 6 to 10 participants at up to 7 centers with appropriate inpatient facilities in the United States. Eligible participants must have clinically stable disease of mild to moderate severity, with good to moderate functional status. Participants may not be taking more than 2 medications from the following classes:

- Endothelin receptor antagonists (eg ambrisentan, bosentan, macitentan),
- Phosphodiesterase type 5 inhibitors (eg sildenafil, tadalafil)
- Guanylate cyclase stimulator (eg riociguat)

It is expected that the site will recruit appropriate potential participants according to the criteria in [Section 5.1](#) and [Section 5.2](#). Prospective approval of protocol deviations to recruitment and enrollment criteria, also known as protocol waivers or exemptions, is not permitted.

The study inclusion and exclusion criteria include thresholds of selected RHC and ECG parameters that must be met at Baseline or the participant will not be considered eligible for the study. In this case, the participant is to be reported as a Screen Failure ([Section 5.4](#)).

5.1. Inclusion Criteria

Participants are eligible to be included in the study only if they meet all of the following criteria^a:

Age:
1. Participant must be ≥ 18 years of age at the time of signing the informed consent.
Type of Participant and Disease Characteristics

2. Participants must have a diagnosis of WHO Group 1 PH (PAH) with the following characteristics (Galie et al., 2016):
 
 a. Etiology of idiopathic, heritable, drug/toxin-induced or connective tissue disease (CTD)-related PAH; b. Right heart catheterization within the last 3 years with the following hemodynamic findings: 
 - Mean pulmonary arterial pressure (mPAP) > 20 mmHg at rest, - Pulmonary capillary wedge pressure (PCWP) ≤ 15 mmHg, and - Pulmonary vascular resistance (PVR) of ≥ 3 Wood Units (WU) 
3. PAH diagnosis for at least 1 year
 
4. New York Heart Association (NYHA)/WHO Functional capacity Class I-III
 
5. No change in pulmonary hypertension medications (e.g., ambrisentan, bosentan, macitentan, sildenafil, tadalafil, riociguat) or dosage for at least 90 days prior to Screening.
 
6. No change in diuretic use or dosage for at least 30 days prior to Screening

7. Documented predicted percent forced vital capacity (FVC) > 70% within 1 year of Screening. If not available, pulmonary function testing will be performed at Screening ([Table 1](#)).
8. At least 2 of the following European Respiratory Society/European Society for Cardiology (ERS/ESC) low risk criteria:
 - a. NT-pro-BNP concentration < 300 ng/L within 6 months of Baseline (if not available will be obtained at Screening, [Table 1](#)).
 - b. Historical documentation of 6- minute walk distance (6MWD) > 440 meters within 6 months prior to Baseline. If not available will obtain 6MWD test at Screening ([Table 1](#)).
 - c. Right atrial pressure (RAP) < 8 mmHg within 1 year prior to Baseline
 - d. Cardiac Index (CI) $\geq 2.5 \text{ L/min} \cdot \text{m}^2$ or mixed venous oxygen saturation (MVO₂) > 65% within 1 year prior to Baseline
9. Right heart catheterization at Baseline with the following hemodynamic findings:
 - a. Mean pulmonary arterial pressure (mPAP) > 20 mmHg at rest,
 - b. Pulmonary capillary wedge pressure (PCWP) $\leq 15 \text{ mmHg}$, and
 - c. Pulmonary vascular resistance (PVR) of $\geq 3 \text{ Wood Units (WU)}$

Weight

10. Body mass index (BMI) within the range 19.0 - 32.0 kg/m² (inclusive).

Sex and Contraceptive/Barrier Requirements

11. Male participants: Male participants and their female partners of childbearing potential must agree to use highly effective contraception from Study Day 1 to at least 90 days after dosing.
12. Female participants: Women of child-bearing potential (WOCPB, defined as premenopausal, not surgically sterile for at least 3 months prior to Screening) must use a highly effective contraception method and agree to be tested for pregnancy from at Screening, Baseline, and 30 days after dosing.

See [Section 10.4](#) for contraceptive guidance.

Informed Consent

13. Capable of giving signed informed consent as described in [Section 10.1.5](#) which includes compliance with the requirements and restrictions listed in the informed consent form (ICF) and in this protocol.

^a Please note that participants who enroll in the optional EUT period beyond the initial 30 day follow-up period will be screened to confirm that they still meet inclusion/exclusion criteria. Please refer to [Table 5](#).

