Time	--	0	30 (\pm 10) mins	60 (\pm 10) mins	2 h (\pm 20) mins	4 (\pm 1) h	8 (\pm 2) h	24 (\pm 2) h	48 (\pm 4) h	
PK sampling ^a	X	--	X	X	X	X	X	X	X	X
Biomarker sampling ^b	X	--	--	--	--	X	X	--	--	

^a PK sampling for treprostinil palmitil and treprostinil; each PK sample will be approximately 10 mL.

^b Each biomarker sample will be approximately 5 to 7 mL.

Table 4: Schedule for Optional Procedures and Assessments, Inpatient Treatment Period, INS1009-201

Inpatient Treatment Period (Study Day 1 to Study Day 2)										
	Pre-TPIP Administration	TPIP Administration	Post-TPIP Administration							
Procedure	Study Day 1 Baseline	Time 0	2-8 hr	4-8 hr						
Transthoracic echocardiogram (LVEF, TVR maximum velocity, TAPSE, end diastolic right ventricular volume)	X	--	X	--						
Pulmonary CT scan (total blood volume, blood volume in vessels < 5 mm ²)	X	--	--	X						
--	Pre-TPIP Administration	TPIP Administration	--							
--	Study Day 1 Baseline	Time 0	30 mins	60 mins	90 mins	2 h	3 h	4 h	8 h	24 h
Resting respiratory gas exchange assessment ^a (respiratory rate, minute ventilation, VCO ₂ , ETO ₂ , ETCO ₂ , SpO ₂)	X	--	X	X	X	X	X	--	X	X

^a Resting respiratory gas assessment parameters are collected at the same time points as RHC parameters.

NOTE: Parameters to be measured for each procedure are in parentheses.

CT=computerized tomography; ETCO₂=end tidal carbon dioxide concentration; ETO₂=end tidal oxygen concentration; LVEF=left ventricular ejection fraction; SpO₂=arterial blood oxygen saturation; TAPSE=tricuspid annular plane systolic excursion; TVR=tricuspid valve regurgitation; VCO₂=carbon dioxide production

Table 5: Schedule of Activities for Screening and Follow-up, Extended Use Treatment Period, INS1009-201

Procedure	Screening ^a	Follow-up
	EUT Study Day 1 (\pm 3 days)	EUT Study Day 142 (\pm 3 days)
Informed Consent	X	--
Inclusion/Exclusion Criteria	X	--
Demographics	X	--
Smoking Status	X	--
Height, Weight, BMI Calculation	X	--
Prior/Concomitant Medications	X	X
Urine Pregnancy Test (WOCBP only)	X	X
Hematology, Clinical Chemistry (Table 7)	X	--
NT-pro-BNP Sample (if needed, Section 5.1)	X	--
Vital Signs	X	--
6 Minute Walking Distance Test (if needed, Section 5.1)	X	--
Adverse Events ^b	X	X

^a Participants will only be screened at EUT Day 1 if they enter the EUT period beyond 30 days after beginning the single-dose period (e.g., beyond the initial 30 day follow-up period).

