4.1.4. Optional Extended Use Treatment Period

All participants will be allowed to enter the optional 16 week EUT period after the completion of the inpatient treatment period and final PK sample collection. Entry into the optional EUT period will be at participant and Investigator discretion. A gap between the inpatient treatment period and EUT period is expected, but not required, and can be up to 6 months.

After collection of the final PK sample, all participants will be allowed optional continued access to IMP for 16 weeks (includes a 3-week titration period) from first administration in the EUT period. At the Investigator's discretion, participants may undergo a study drug taper for up to 2 weeks after the Week 16 visit to help facilitate a safe withdrawal from study drug.

Participants will be screened to ensure they meet inclusion and exclusion criteria if they enter the EUT period more than 30 days after beginning the single-dose period (e.g., beyond the initial 30 day follow-up period) ([Table 5](#)).

Participant in-clinic study visits will be scheduled for EUT Baseline (EUT Day 1), EUT Week 2, EUT Week 3, EUT Week 5, EUT Week 10, and EUT Week 16.

The CT scan will be performed according to instructions provided by the CT scan vendor.

There will be a second safety follow-up visit 30 days (\pm 3 days) after EUT Week 16 for participants who elect to enter the EUT period.

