8.2.5. Pregnancy Testing

8.2.5.1. Single-dose Period

Willingness of WOCBP to undergo serum or urine pregnancy testing is a study eligibility criterion. Pregnancy tests will be conducted at screening, baseline, and Study Day 30. WOCBP

participants will be provided a home pregnancy test kit with instructions to conduct and report test results at the Study Day 30 follow-up visit which is scheduled to be by telephone call or telemedicine. If the participant elects to enter the optional EUT period and the remote safety follow-up visit overlaps with the start of the EUT period, the results of a urine pregnancy test will be recorded at the first visit in the extended treatment period.

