8.3.5. Pregnancy

Details of all pregnancies that occur in WOCBP participants within 30 days after TPIP administration will be collected. Male participants with WOCBP partners must continue to use contraception for 90 days after TPIP administration and report any pregnancies that occur within that time period.

If a pregnancy is reported, the Investigator will record pregnancy information on the appropriate form and submit it to Insmed within 24 hours of learning of the pregnancy in a female participant or female partner of male participant and after obtaining the necessary signed informed consent from the female partner.

While pregnancy itself is not considered to be an AE or SAE, any pregnancy complication or elective termination of a pregnancy for medical reasons will be reported as an AE or SAE.

Abnormal pregnancy outcomes (e.g., spontaneous abortion, fetal death, stillbirth, congenital anomalies, ectopic pregnancy) are considered SAEs and will be reported as such.

Any female participant who becomes pregnant while participating in the study will be discontinued from the study.

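### The male contraception and pregnancy-reporting periods are still tied to a single dose, although Amendment 1 added 16 weeks of daily dosing

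*Protocol*

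**What the plan says.** Inclusion criterion 11 (Protocol Section 5.1) applies to men in the trial and to any partner who could become pregnant. It says that they "must agree to use highly effective contraception from Study Day 1 to at least 90 days after dosing". Section 8.3.5 repeats the period and adds a reporting duty: male participants with partners of childbearing potential "must continue to use contraception for 90 days after TPIP administration and report any pregnancies that occur within that time period". For female participants the same section says: "Details of all pregnancies that occur in WOCBP participants within 30 days after TPIP administration will be collected".

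None of these sentences names the dose. They match the corresponding sentences in Protocol version 1.0, when there was only one dose to count from.

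The current design has many doses. Section 4.1.4 opens the EUT period to all participants after the final PK sample, for 16 weeks of IMP. It says of the timing: "A gap between the inpatient treatment period and EUT period is expected, but not required, and can be up to 6 months". It also allows that "participants may undergo a study drug taper for up to 2 weeks after the Week 16 visit".

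Eligibility is not always re-checked at EUT entry. Footnote a of Table 5 (Section 1.4) states: "Participants will only be screened at EUT Day 1 if they enter the EUT period beyond 30 days after beginning the single-dose period".

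**The concern.** A rule written for one dose now governs a course of up to 126 daily doses after it. A site that takes the sentences at face value can count from the single dose, and the text around them supports that:

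- Inclusion 11 starts the clock on Study Day 1.
- Inclusion 12, directly below, has women "agree to be tested for pregnancy from at Screening, Baseline, and 30 days after dosing". There *dosing* must be the single dose, because Section 8.2.5.1 gives the schedule as: "Pregnancy tests will be conducted at screening, baseline, and Study Day 30".
- Elsewhere *TPIP administration* usually means the inpatient dose (Tables 2 to 4, Section 8.3.1), while the EUT text mostly speaks of *IMP* or *study drug* (Sections 1.3.2.2, 4.1.4, 6.1.2).

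Amendment 1 updated nearby rules. Concomitant therapy now runs to end of study (Section 6.8), and pregnancy testing gained an EUT subsection (8.2.5.2), for women only. No EUT section resets the male period.

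What is at stake is partner safety and consistency between sites. A man's contraception duty, and his duty to report a partner's pregnancy, could lapse while he is inhaling the drug daily. Female participants have tests every 30 days through EUT treatment and follow-up; partners have no scheduled test.

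**Working it through.** This is calendar arithmetic; no power or error rate is involved.

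**Inputs**
- Single dose on Study Day 1. Section 4.1 puts 48 hours post-dose on Study Day 3, so *n* days after the dose is Study Day 1 + *n*.
- Earliest EUT entry: after the 48-hour sample, Study Day 3 (Section 4.1.4).
- Entry without re-screening: taken as up to Study Day 30 (Table 5, footnote a).
- Last regular EUT dose: taken as EUT Day 112, the Week 16 visit. A full taper adds 14 days.

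**The plan's own figure.** 16 × 7 = 112, and 112 + 30 = 142. This agrees with the 142 days in Section 4.1 and with EUT Day 142 in Table 6.

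**Counting from the single dose.** The period ends on Study Day 1 + 90 = 91. If EUT Day 1 is Study Day E, then Study Day 91 is EUT Day 92 − E, the last regular dose is on Study Day E + 111, and the dosing days left over are (E + 111) − 91.

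| EUT entry | Study Day 91 is | Last dose (with taper) | Dosing days after Day 91 (with taper) |
|---|---|---|---|
| E = 3 | EUT Day 89 | Study Day 114 (128) | 23 (37) |
| E = 30 | EUT Day 62 | Study Day 141 (155) | 50 (64) |

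The visit window does not change this. With E = 3 and the Week 16 visit 3 days early, the last dose is still on Study Day 111. No full EUT course finishes by Study Day 91.

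**Counting from the first EUT dose.** The period ends on EUT Day 91, still 112 − 91 = 21 days short (35 with a full taper).

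**Counting from the last dose.** The period ends on EUT Day 112 + 90 = 202, or 126 + 90 = 216 with a full taper. No dosing day is left out.

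**Distance between the first and last of these readings**
- E = 3: 114 + 90 − 91 = 113 days (127 with taper).
- E = 30: 141 + 90 − 91 = 140 days (154 with taper).

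**Female collection window.** From the single dose it ends on Study Day 1 + 30 = 31. From the last dose it would end on EUT Day 112 + 30 = 142, or 156 with a full taper.

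**The case against.** The best counter-argument is that a sensible site would never count from the single dose. *At least* sets a minimum, and *TPIP administration* can cover EUT doses. Section 8.3.5 carries no single-dose label, whereas Sections 8.2.5.1 and 8.3.1 do carry one. Amendment 1 also edited 8.3.5: the discontinuation sentence now applies to any woman who becomes pregnant during participation, with no restriction to the time before dosing. Section 10.4 ties contraception to local regulations and describes abstinence as lasting for the study, which for an EUT participant ends at EUT Day 142. The consent form is not shown and may be clearer.

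This shows that the last-dose reading is open. It does not show that the text selects it. Section 10.4 gives no post-dose end date, and the edit to 8.3.5 left both windows untouched.

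Three parts of the objection do limit the point:

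- **Late entrants.** A reader might infer that a man entering EUT after Study Day 91 has all 112 dosing days (126 with taper) uncovered. The documents do not support that. Anyone entering more than 30 days after the single-dose period began is screened against the criteria, and inclusion 11 asks for a forward-looking agreement. He would probably be asked to agree for the dosing about to start, although the sentence put to him is the same unanchored one.
- **Reporting.** A reader might infer that partner pregnancies after Day 91 go unrecorded. Only the man's own duty has a window. Under Section 8.3.5 the Investigator submits any reported partner pregnancy within 24 hours of learning of it, once the partner consents. EUT participants also have six clinic visits and a follow-up contact.
- **Numbers.** Section 2 puts PAH incidence in women at about 4 times that in men. If enrolment mirrored this (an assumption), men would be one fifth of 6 to 10 participants, or about 1 to 2.

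**Conclusion.** The rule is wrong as written, because it is a single-dose rule left in a multiple-dose protocol. The severity is minor. Read literally from the single dose, the male period ends on Study Day 91. For men entering EUT between Study Days 3 and 30 without re-screening, that leaves 23 to 50 scheduled dosing days (37 to 64 with a full taper) and all of the post-dose period outside it. It would go too far to say that the protocol definitely ends contraception during treatment: on the last-dose reading nothing is uncovered, and the text does not choose between the two.

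The figures assume a full EUT course with the last regular dose on EUT Day 112. No endpoint, dose decision or analysis is affected, and the reporting gap is partial.

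**What to change.** In inclusion 11 and Section 8.3.5, state the male period as: *from Study Day 1 through at least 90 days after the last dose of study IMP; for participants who enter the EUT period, from EUT Day 1 through at least 90 days after the last EUT or taper dose*. The second clause covers a man whose first period has run out before he starts EUT. In Section 8.3.5, set the female collection window as: *from first dose through 30 days after the last dose of study IMP*. Last dose of study IMP is already the protocol's own reference point in the TEAE definition (Section 10.3.1).

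The cost is protocol wording, plus consent-form wording if it repeats the protocol. No visit or test is added. The male period would end 202 − 142 = 60 days after the last EUT contact (74 with a full taper). That is no new burden in kind: for single-dose participants the present period already ends 91 − 30 = 61 days after the Study Day 30 call. The female window would end on EUT Day 142, or 14 days later with a full taper.

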5.2. Exclusion Criteria

Participants are excluded from the study if they meet any of the following criteria^a:

Medical Conditions

 1. Any PH other than idiopathic, hereditary, drug/toxin-induced, or connective tissue disease (CTD) associated PAH (e.g., congenital heart disease-associated PAH, portal hypertension-associated PAH, PH belonging to Groups 2 through 5) 2. Allergy, or documented hypersensitivity or contraindication, to the ingredients of treprostinil palmitil inhalation powder (TPIP) or treprostinil (TRE). 3. Previous intolerance to prostacyclin analogs or receptor agonists (e.g., selexipag) per Investigator discretion 4. History of anaphylaxis or previously documented hypersensitivity reaction to any drug per Investigator discretion 5. QTcF interval > 480 ms on resting ECG at Baseline 6. History of heart disease including left ventricular ejection fraction (LVEF) ≤ 40% or clinically significant valvular, constrictive, or atherosclerotic heart disease (myocardial infarction, etc) 7. Abnormal renal function (estimated glomerular filtration rate < 30 mL/min/1.73m²) at Screening. 8. Active liver disease or hepatic dysfunction manifested as: 
 a. Elevated liver function test results (ALT or AST > 2 × ULN) at Screening b. Bilirubin > 1.5 × ULN (isolated bilirubin > 1.5 × ULN; ULN is acceptable if bilirubin is fractionated and direct bilirubin < 35%) at Screening. c. Known hepatic or biliary abnormalities, not including Gilbert's syndrome or asymptomatic gallstones at Screening. 9. History of HIV infection/positive HIV serology test result at Screening. 10. History of active/chronic Hepatitis B or C/ positive hepatitis B or C serology test result at Screening 11. History of abnormal bleeding or bruising. 12. Known or suspected immunodeficiency disorder, including history of invasive opportunistic infections (e.g., tuberculosis, histoplasmosis, listeriosis, coccidioidomycosis, pneumocystosis, aspergillosis) despite infection resolution, or otherwise recurrent infections of abnormal frequency, or prolonged infections suggesting an immune-compromised status, as judged by the Investigator.

13. Active and current symptomatic infection by SARS CoV 2. Additional COVID 19 restrictions per institutional guidelines (See also [Section 10.1.3.1.3](#))
14. Participants with current or recent (past 4 weeks) lower respiratory tract infection (may be re-screened at appropriate time ([Section 5.4](#))
15. History of malignancy in the past 5 years, with exception of completely treated in situ carcinoma of the cervix and completely treated non-metastatic squamous or basal cell carcinoma of the skin.

Concomitant Therapy

16. Participants receiving triple combination therapy for PAH consisting of endothelin receptor agonists, phosphoesterase type 5 inhibitors, and guanylate cyclase stimulators (riociguat).
17. Participants receiving prostanoids/prostacyclin agonists
18. Participants receiving potent CYP2C8 inhibitors, such as gemfibrozil
19. Other prior/concomitant therapies are allowed/disallowed at the Investigator's discretion

Prior/Concurrent Clinical Study Experience

20. Have participated in any other interventional clinical studies within 30 days of Baseline

Diagnostic assessments

21. Any clinically significant abnormal laboratory, value, test result, or physical examination finding at Screening; diseases or diagnoses/disorders that, in the opinion of the Investigator, may put the participant or others at risk by participating in the study, interfere with the participant's treatment and assessment, or influence the results of the study; or have compliance issues with the study.

Other Exclusions

22. Current or history of substance and/or alcohol abuse per Investigator assessment
23. Current user of cigarettes or e-cigarettes
24. Pregnant or breastfeeding.

^a Please note that participants who enroll in the optional EUT period beyond the initial 30 day follow-up period will be screened to confirm that they still meet inclusion/exclusion criteria. Please refer to [Table 5](#).

